## **Primary Safety Endpoints**

The primary safety endpoints will be assessed on the adverse events (AEs) and serious adverse events (SAEs) that are observed throughout the trial.

## **Treatment of Acute Renal Allograft Rejection**

Initial treatment for biopsy-confirmed acute rejection for all subjects will be pulse corticosteroids (methylprednisolone 500 mg IV x 3 days), tapered to a dose of 20 mg prednisone by day 7, unless the severity of the initial episode warrants use of anti-T-lymphocyte antibody (OKT3 or Thymoglobulin). Recurrent rejection will be treated with anti-T-lymphocyte antibody (OKT3 or Thymoglobulin).

## **Subject Selection and Withdrawal**

The study will be conducted at Northwestern Medical Faculty Foundation/Northwestern Memorial Hospital/ Northwestern University and subjects will be recruited from the patients seen in the Division of Solid Organ Transplantation. A total of 400 recipient subjects will be screened and we expect that 275 recipients will be prospectively studied. The study will be conducted in recipients of living donor kidneys and deceased donor kidneys. Patients who satisfy the following inclusion/exclusion criteria will be eligible for the study.

### **Inclusion Criteria**

- 1) Subjects should be adults  $\geq 18$ -  $\leq 70$  years of age
- 2) Subjects can be either gender or of any ethnic background
- 3) Subjects should be single organ recipients (kidney only)
- 4) Subjects must be able to understand the protocol and provide informed consent.

### **Exclusion Criteria**

- 1) Subjects with ESRD secondary to primary FSGS (focal segmental glomerulonephritis).
- 2) Inability to comply with study procedures
- 3) Inability to sign the informed consent
- 4) Subjects with a significant or active infection
- 5) Subjects who are pregnant or nursing females
- 6) Subjects with a history of severe hyperlipidemia not controlled with statins, patients with at total cholesterol of  $> 400$  mg/dl
- 7) Subjects with a platelet count  $< 100,000\text{mm}^3$  WBC  $< 2,000\text{mm}^3$
- 8) Subjects with severe proteinuria at the time of randomization ( $> 2\text{gm/day}$ )
- 9) Subjects with more than 2 episodes of acute cellular rejection post transplantation will be excluded from this study
- 10) An estimated GFR  $< 40$  cc/min (This will be calculated by MDRD or by Cockcroft-Gault formulas, which are both are commonly used formulas for estimated GFR.)
- 11) A history of malignancy during the post-transplant period (other than treated basal cell cancer and/or squamous cell cancer)
- 12) Subjects, who, due to the existence of a surgical, medical or psychiatric condition, other than the current transplant, which in the opinion of the investigator, precludes enrollment into this trial
- 13) A history of ACR during the most recent previous 3 months prior to randomization

\*\*Other: prior to approaching any individual who has undergone desensitization procedures prior to transplant, we must first check with Dr. [name]

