### **Research Objective**

The aim of the present study is to prospectively investigate the impact of CI conversion (tacrolimus→sirolimus) between 6 and 24 months post-transplant on the incidence of acute cellular rejection, renal allograft function and lymphocytes function.

Primary aim of the study is:

to investigate the impact of CI conversion (tacrolimus→sirolimus) on the incidence of acute cellular rejection.

Secondary aims of the study are:

- i) evaluate whether CI conversion (tacrolimus→sirolimus) contributes positively or negatively on the renal allograft function calculated with e-GFR and proteinuria;
- ii) patient and graft survival ;
- iii) evaluate if CI conversion impacts on lipid profile, incidence of hypertension, malignancies, and opportunistic infections and post-transplant DM;
- iv) evaluate possible modifications of lymphocytes function before and after conversion (tacrolimus→sirolimus)
- v) assess tubular toxicity by evaluating urinary biomarkers

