### **Randomization**

For this research study, between 6 and 24 months post-transplant we plan to prospectively randomize 2:1 renal transplant patients to either:

- Continue with tacrolimus and MMF or
- Substitute tacrolimus with sirolimus and continue MMF

A total of 400 pts. are expected to be screened for the randomization and we expect to be able to randomize 275 renal transplant patients into this protocol.

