### **Data Collection**

The following data will be collected at the time of randomization:

Recipient demographics- such as age at transplantation, sex and race.

Clinical history- Causes of end-stage renal disease, past medical history

Transplant related information- donor age, cadaveric versus living kidney transplant, histocompatibility and cross match data, viral serology, history of acute rejection and delayed graft function, use of induction therapy and immunosuppressants, use of ACEI and/or ARB, level of renal allograft function- estimated GFR (e-GFR(12) using MDRD formula, proteinuria.

Peripheral blood leukocytes will be obtained from renal transplant recipients for baseline (prior to randomization) lymphocytes functional activity and characterization of lymphocytes subpopulations by flow cytometry analysis.

Peripheral donor leukocytes (from living donor patients) will also be obtained at the time of randomization. These donor leukocytes will be used as stimulator cells to study the functional activity of the recipient's lymphocytes function.

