## **Biopsy**

Chronic nephrotoxicity from calcineurin-inhibitors (CI) has been implicated as a principal cause of post-transplant renal dysfunction and it is characterized by an irreversible and progressive tubular atrophy, interstitial fibrosis, and focal hyalinosis of small renal arteries and arterioles. Furthermore, chronic nephrotoxicity from CI has been documented in all non-renal transplants and the chronic renal failure secondary to the use of CI has been associated with an increase in mortality by a factor of more than four.

The present proposal is to identify those subjects already participating in this study who are willing to undergo a kidney biopsy with the aim of evaluating renal allograft pathology and renal allograft tissue gene expression profiles of the two groups of patients maintained on Tacrolimus/ MMF or switched to SRL/MMF. Performing kidney biopsies on the subjects who consent for the procedure will allow us to address the effect of immunosuppressive modifications on renal allograft pathology at 24 months post randomization. We also plan to obtain renal allograft biopsies at 12 months post-transplant (standard of care) in order to establish a baseline parameter for to compare the 24 month sample. An additional biopsy at 48 months will allow us to examine long term results of graft function. We also plan to obtain renal allograft biopsies to be stored in RNA later to further extend our knowledge on the effect of CI free immunosuppression on gene expression profiles.

Obtaining renal allograft tissue samples at 24 and 48 months post randomization can have potential important ramifications to help explain the mechanisms of fibrosis and tubular atrophy typically associated with CI and the role of CI elimination with the substitution of SRL. All data will then be analyzed comparing gene expression profiles of peripheral blood (Paxgene tubes are routinely collected at the different time points as part of the original study). Based on power analysis, we will perform 24 and 48 months post randomization biopsies in 70% of the total subjects enrolled in the study (approximately 46 subjects from the tacrolimus/MMF group and approximately 93 subjects from the sirolimus/MMF group).

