## **Statistical Analysis**

Once the 2 groups of renal transplant patients are identified, two sample t tests will be used to compare differences in continuous variables between groups; chi square tests will be used to compare differences in discrete variables. Multivariable logistic regression analysis will be also performed to identify the combination of clinical variable that are significantly associated with the development of acute rejection and renal allograft function after conversion from tacrolimus →sirolimus.

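### The primary comparison of acute rejection is unadjusted although rejection history is recorded at randomisation; adjusting for it gains a little power, and a by-history table shows what pooling leaves unseen

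*Combined protocol and SAP*

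**What the plan says.** The primary aim under Research Objective is "to investigate the impact of CI conversion (tacrolimus→sirolimus) on the incidence of acute cellular rejection". Two exclusion criteria concern earlier rejection. Item 9 states "Subjects with more than 2 episodes of acute cellular rejection post transplantation will be excluded from this study", and item 13 removes anyone with "A history of ACR during the most recent previous 3 months prior to randomization". Subjects with none, one or two past episodes can therefore enter, provided that none occurred in the last 3 months.

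The Data Collection section lists "history of acute rejection and delayed graft function" among the items recorded at randomisation. The Randomization section says "we plan to prospectively randomize 2:1 renal transplant patients to either" and names no stratification factor.

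For a yes/no outcome, the Statistical Analysis section gives one between-group method: "chi square tests will be used to compare differences in discrete variables". It then adds: "Multivariable logistic regression analysis will be also performed to identify the combination of clinical variable that are significantly associated with the development of acute rejection". No covariates are listed. The text does not say whether treatment arm is a term in that model or whether both arms enter it. No subgroup or interaction analysis is named.

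**The concern.** Past rejection is the same kind of event as the primary outcome, so it is a plausible strong predictor of it. The protocol treats it as relevant to eligibility and collects it at baseline, but the primary comparison as written makes no use of it. Two things follow.

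First, adjusting for a prognostic baseline variable usually gains some power at almost no cost, and the plan forgoes that gain.

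Second, a single pooled comparison says nothing about the effect in subjects who have already rejected. The Background section reports a retrospective analysis that concluded conversion was not associated with more rejection. A non-significant pooled result here could be read the same way and applied to previously rejecting subjects, whose own result the plan never shows.

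**Working it through.** **The plan's own figure.** The 275 to be randomised cannot be reproduced: the documents give no significance level, power, rejection rate or effect size with it.

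**Inputs from the documents.** 275 subjects, randomised 2:1. The direction is inferred from the biopsy counts, "approximately 46 subjects from the tacrolimus/MMF group and approximately 93 subjects from the sirolimus/MMF group", a ratio of about 1:2. Hence 275/3 ≈ 92 on tacrolimus and 2 × 275/3 ≈ 183 on sirolimus.

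**Inputs assumed.** Two-sided 5% level; tacrolimus rejection risk of 8% without prior rejection; prior-rejection share of 5 to 30%; prognostic odds ratio of 2 to 5.

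**Method.** Trials were simulated at 183 v 92 (40,000 per scenario unless stated). An uncorrected chi-square was compared with a Mantel-Haenszel test stratified by any prior rejection.

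**Step 1: validity.** With no treatment effect, the chi-square rejects in 4.7% of trials and the stratified test in 4.8 to 4.9%. Both hold the 5% level.

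**Step 2: power with a treatment odds ratio of 2.5 in both strata.**

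| Prior-rejection share | Prognostic odds ratio | Chi-square | Stratified | Gain (points) |
|---|---|---|---|---|
| 10% | 2 | 63.7% | 64.1% | 0.4 |
| 10% | 3 | 64.4% | 65.3% | 0.9 |
| 10% | 5 | 64.4% | 66.8% | 2.4 |
| 20% | 3 | 67.9% | 69.6% | 1.7 |
| 20% | 5 | 68.5% | 72.6% | 4.1 |
| 30% | 3 | 71.3% | 73.4% | 2.1 |
| 30% | 5 | 71.8% | 76.3% | 4.5 |

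Over the full grid, including a 5% share and a treatment odds ratio of 3, the gain runs from 0.1 to 4.5 points.

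A separate scenario takes a 15% share, with risks of 8% v 18% (tacrolimus v sirolimus) without prior rejection and 30% v 50% with it. Power is 64.5% crude and 67.9% stratified (20,000 trials), a gain of 3.4 points. Two repeat runs of 40,000 gave 65.4% v 68.6% and 65.0% v 68.4%. The gain shrinks when the assumptions are less favourable:

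- With a 5% share, power goes from 62.8% to 64.3%.
- With a 15% share but risks of only 15% v 30% after prior rejection, it goes from 65.0% to 65.7%.

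**Step 3: chance imbalance in the 15% scenario.** The SD of the between-arm difference in prior-rejection share is √[0.15 × 0.85 × (1/92 + 1/183)] = 0.046. A 2-SD imbalance shifts the crude risk difference by about 2 × 0.046 × (0.30 − 0.08) = 0.020, or 2 points. The overall risks are 0.85 × 0.08 + 0.15 × 0.30 = 0.113 and 0.85 × 0.18 + 0.15 × 0.50 = 0.228. The SD of the crude difference is therefore √[0.113 × 0.887/92 + 0.228 × 0.772/183] = 0.045. Even a 2-SD imbalance moves the estimate by less than half of its own SD.

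**Step 4: an excess confined to prior rejectors.** Take a 15% share, 8% risk in both arms without prior rejection, and 20% v 50% with it (the tacrolimus risk here is 20%, not the 30% of Step 2). The pooled difference is 0.15 × (0.50 − 0.20) = 0.045. Power is 17.0% crude and 19.5% stratified.

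With 21% v 57% among prior rejectors and 8% elsewhere:

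| Share | Chi-square | Stratified | Interaction test | Test within prior rejectors |
|---|---|---|---|---|
| 10% | 12.5% | 14.7% | 24.8% | 30.7% |
| 20% | 33.7% | 40.1% | 45.3% | 69.2% |

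At the 10% share the overall risks are 9.3% v 12.9%, so a large excess in one stratum looks small overall. Stratifying the test barely helps. Only a display by stratum shows it.

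**Step 5: precision of that display.** At a 15% share the prior-rejection stratum has 0.15 × 92 ≈ 14 and 0.15 × 183 ≈ 27 subjects. For risks of 20% v 50%, the 95% half-width is 1.96 × √(0.20 × 0.80/14 + 0.50 × 0.50/27) = 0.28. The interval is about ±28 points around a difference of 30.

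**The case against.** The strongest case for leaving the plan alone is that randomisation already makes the chi-square valid, so choosing an adjusted test for a few points of power is partly preference. That largely stands. A reader might infer that pooling biases the test or leaves it exposed to imbalance. Step 1 shows that the error rate is intact, and the sampling variance already includes chance imbalance.

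A reader might also infer that a large amount of power is lost. The documents give neither the share with prior rejection nor any rate, and no plausible combination examined gave more than 4.5 points.

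A third tempting reading is that a stratified test would uncover harm limited to prior rejectors. It would not: it also pools the strata into one effect, and power moves only from 17.0% to 19.5%. The table by stratum does that job, and imprecisely.

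Finally, the planned regression might turn out to include arm and prior rejection. The text does not rule this out, so it would be too strong to say that the model ignores them. What can be said is that its covariates and its role are unspecified, and that its stated purpose is to find predictors rather than to estimate an adjusted arm effect. An adjusted primary comparison is therefore still not pre-specified.

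**Conclusion.** The point holds as a low-cost improvement to a valid analysis. The plan records a likely strong predictor of its primary outcome and specifies no arm comparison that uses it. The cost is about 0 to 4.5 points of power over the assumed ranges, and about 3 points in the 15% scenario. It is about 1 point or less if at most 10% of subjects have prior rejection and the prognostic odds ratio is 3 or below. Separately, the effect in previously rejecting subjects would go unreported, and a sizeable excess there could pass unnoticed in the pooled result. Every rate and share behind these figures is an assumption, as is the prognostic strength of prior rejection.

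**What to change.** In the Statistical Analysis section:

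1. Make the primary between-arm analysis of acute cellular rejection, in all randomised subjects, adjusted for prior rejection (none v any). Use either a Mantel-Haenszel stratified test with a common odds ratio or a logistic model containing arm and prior rejection. The odds ratio is the better scale for pooling here: in the 15% scenario of Step 2 the stratum odds ratios are similar (2.5 and 2.3), while the risk differences are 10 and 20 points.
2. Keep the unadjusted chi-square as a supportive analysis.
3. Report rejection risk by arm, and the arm difference with a 95% interval, within each prior-rejection stratum. Label this descriptive.
4. State that the predictor-search regression is separate from the primary analysis.

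This changes wording only. The history is already collected, although the Data Collection section records acute rejection in general; whether an episode was cellular would come from the eligibility check under items 9 and 13. The downside is the small prior-rejection stratum, whose estimate should not be read as confirmatory in either direction.

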### **Subject Recruitment and Screening**

The study will be conducted at Northwestern Medical Faculty Foundation/Northwestern Memorial Hospital/ Northwestern University and subjects will be recruited from the patients seen in the Division of Solid Organ Transplantation. A total of 400 recipient subjects will be screened and we expect that 275 recipient patients to be prospectively studied.

## **Early Withdrawal of Subjects**

### **When and How to Withdraw Subjects**

Subjects may withdraw from the clinical trial at any time for any reason with no prejudice to their medical care. Subjects may also be stopped in the study without their consent if their medical care requires they be. Also, the Institutional Review Board (IRB) may stop the study at any time and all subjects will be returned to taking tacrolimus and followed for safety. Subjects will be informed of why they are being stopped.

Subjects non-compliant with medications and clinic follow-ups will be withdrawn from the study.

Subjects with post-transplant complications such as malignancy or infections that require modification or withdrawal of maintenance immunosuppression will be withdrawn from the study.

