### **Data Collection and Follow-up for Withdrawn Subjects**

Even though subjects may be withdrawn prematurely from the study, an attempt will be made to collect at least survival data on such subjects throughout the protocol defined follow-up period. Such data is important to the integrity of the final study analysis, since early withdrawal could possibly be related to the safety profile of the study. If a subject withdraws consent to participate in the study, attempts will be made to obtain permission to record at least survival data up to the protocol-described end of subject follow-up period.

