### **Post-study Adverse Event**

All unresolved adverse events should be followed by the investigator until the events are resolved, the subject is lost to follow-up, or the adverse event is otherwise explained. At the last scheduled visit, the investigator should instruct each subject to report any subsequent event(s) that the subject, or the subject's personal physician, believes might reasonably be related to participation in this study.

The investigator will notify the drug manufacturer, IRB, and FDA of any death or adverse event occurring at any time after a subject has discontinued or

terminated study participation that may reasonably be related to this study. The drug manufacturer, IRB, and FDA will also be notified if the investigator should become aware of the development of cancer or of a congenital anomaly in a subsequently conceived offspring of a subject that has participated in this study.

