### **Recording of Adverse Events**

At each contact with the subject, the investigator/member of investigator's team will seek information on adverse events by specific questioning and, as appropriate, by examination. Information on all adverse events will be recorded in the source document, and also in the appropriate adverse event module of the case report form (CRF). All clearly related signs, symptoms, and abnormal diagnostic procedures results should be recorded in the source document, though should be grouped under one diagnosis.

All adverse events occurring during the study period must be recorded. The clinical course of each event should be followed until resolution, stabilization, or until it has been determined that the study treatment or participation is not the cause. Serious adverse events that are still ongoing at the end of the study period must be followed up to determine the final outcome. Any serious adverse event that occurs after the study period and is considered to be possibly related to the study treatment or study participation should be recorded and reported immediately.

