### **Stopping Rules**

Subjects diagnosed with two acute renal allograft rejection episodes post conversion from tacrolimus to sirolimus will be stopped from participating in the study and will be switched back to tacrolimus.

Subjects that develop significant side effects secondary to sirolimus (severe thrombocytopenia (platelets count <50, 000); severe hyperlipidemia not controlled by the use of statins or other cholesterol lowering agents; worsening proteinuria or severe de-novo proteinuria) will have sirolimus stopped and patients will be switched back to tacrolimus.

Subjects developing post-transplant infections (i.e., UTI, CMV, HSV, EBV, HCV, HBV, HIV, PCP), that in the opinion of the investigator are detrimental to the subject and their participation in this research trial, will be stopped from participating in this study.

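### Subjects withdrawn because a complication changes their immunosuppression have no required follow-up for later rejection, eGFR or proteinuria

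*Combined protocol and SAP*

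**What the plan says.** All references are to the combined protocol and SAP.

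**Exits.** When and How to Withdraw Subjects ties leaving the study to a drug change prompted by a complication: "Subjects with post-transplant complications such as malignancy or infections that require modification or withdrawal of maintenance immunosuppression will be withdrawn from the study". The same section adds: "Subjects non-compliant with medications and clinic follow-ups will be withdrawn from the study". It also lets subjects be stopped without their consent where their medical care requires it. Stopping Rules adds two more exits. One is for infections "that in the opinion of the investigator are detrimental to the subject and their participation in this research trial". The other is for subjects with two rejection episodes, who "post conversion from tacrolimus to sirolimus will be stopped from participating in the study and will be switched back to tacrolimus"; it is written for the sirolimus arm only.

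**A contrasting rule.** For significant sirolimus side effects, Stopping Rules says subjects "will have sirolimus stopped and patients will be switched back to tacrolimus". It states no study exit.

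**Data after exit.** Data Collection and Follow-up for Withdrawn Subjects says that "an attempt will be made to collect at least survival data on such subjects throughout the protocol defined follow-up period", and recognises that early withdrawal may be connected with safety.

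**Outcomes at stake.** Research Objective makes acute cellular rejection the primary aim. eGFR and proteinuria come under secondary aim i, and malignancies and opportunistic infections under aim iii. Post randomization plans 4 years of follow-up in both groups. Statistical Analysis names t tests, chi-square tests and logistic regression, but no analysis population.

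**The concern.** The rule turns a change of treatment into an end of participation. What the protocol then commits to collecting drops to an attempt at survival data, at a point where the subject's rejection risk may be changing.

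Three features make the loss potentially informative. The trigger occurs after randomization, so the assigned drug may influence it. Infection and malignancy are themselves aim iii outcomes. The exit coincides with a change in immunosuppression, which can plausibly alter the chance of rejection. Treatment is also open label, and one infection exit rests on the investigator's opinion, so the frequency and reasons for exit could differ by arm. If they do, the comparison of rejection and graft function no longer rests on the full randomized groups over the planned 4 years.

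**Working it through.** The plan states no figure on this point, so the check is mainly a comparison of sections.

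**1. Exits and what is required afterwards**

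| Trigger | Section | Arm | Study exit stated? |
|---|---|---|---|
| Complication requiring a change in immunosuppression | When and How to Withdraw Subjects | both | yes |
| Non-compliance | same | both | yes |
| Medical care requires it | same | both | yes |
| Infection judged detrimental by the investigator | Stopping Rules | both | yes |
| Two rejections after conversion | Stopping Rules | sirolimus only | yes |
| Sirolimus side effects | Stopping Rules | sirolimus only | no, drug switch only |

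Reading a stop in participation as a withdrawal, the first five all end at the survival floor.

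**2. Capture through safety reporting**

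- To 30 days after the last study treatment (Adverse Event Reporting Period): all adverse events must be recorded, whatever their relatedness. Rejection is included, and so is a laboratory abnormality needing active management.
- After that: "Any serious adverse event that occurs after the study period and is considered to be possibly related to the study treatment" or to participation must be recorded (Recording of Adverse Events). Post-study Adverse Event requires notification of "any death or adverse event occurring at any time after a subject has discontinued" participation, where it may reasonably be related to the study.
- Neither route requires serial eGFR or proteinuria, and later rejection depends on a judgement of relatedness.

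**3. Follow-up at stake per subject.** With 48 months planned and exit at month m, the ceiling is (48 − m)/48:

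- m = 6: 42/48 = 88%
- m = 12: 36/48 = 75%
- m = 24: 24/48 = 50%

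These are upper limits. They apply only if nothing beyond survival is collected.

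**4. Subjects involved.** The documents give no exit rate. Randomization gives 275 subjects at 2:1, and the biopsy counts (about 93 sirolimus, 46 tacrolimus) show that sirolimus is the larger arm: 275 × 2/3 = 183 and 275/3 = 92. At an assumed 5% exit in both arms, about 9 and 5 subjects leave; at an assumed 10%, about 18 and 9.

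**5. Direction.** In each arm let w be the share withdrawn with no earlier rejection, s the rejection rate in the rest, q the later rejection rate in those withdrawn, and d = q − s. True rejection in the arm is (1 − w)s + wq = s + wd. Let subscript 1 denote sirolimus and 0 tacrolimus.

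- If these subjects are left out, the comparison misses w₁d₁ − w₀d₀.
- If they are kept and counted as rejection-free, it misses w₁q₁ − w₀q₀.

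None of w, s or q is in the documents. Moreover, d can be positive, zero or negative: those withdrawn had no rejection up to exit, while the rest of the arm includes early rejections. Neither sign nor size can be set.

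**The case against.** The best case for the plan has five parts.

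- **The survival promise is a minimum, and 4-year follow-up is stated for both groups without exception.** Both are true. But the section written specifically for withdrawn subjects sets the lower commitment, and permission to collect more does not require it.
- **Safety reporting may reach further than it seems.** Tacrolimus and MMF are listed as study drugs, so a withdrawn subject still taking them might be read as inside the 30-day window. The text does not say whether study treatment ends at withdrawal. Even on the generous reading, serial eGFR and proteinuria are not required.
- **Survival data is undefined.** Elsewhere the protocol pairs patient and graft survival, so graft loss may be included. This is possible, and it would leave rejection and graft function uncovered.
- **Subjects attend one centre with monthly labs.** Much of the data may already exist in clinical records. This lowers the likely loss and makes the fix cheap, but availability is not a collection requirement.
- **The complication rule is the same in both arms.** No document shows a difference in exit between arms. This stands: differential loss is a possibility, not a finding.

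A reader might infer more than the text supports:

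- **Every dose change ends participation.** Trough-guided dosing and MMF changes for medical reasons carry no stated exit.
- **Sirolimus side effects remove subjects.** That rule states only a drug switch.
- **Rejections before exit are lost.** They still count. The two-rejection exit therefore loses no first event and is secondary here; what it leaves uncovered is later graft function, in one arm only.
- **There is a bias of known size or sign.** Any such figure would rest wholly on assumed rates.

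**Conclusion.** The point holds as a gap in required data collection. After a complication-driven change in immunosuppression, the protocol mandates study exit and then secures only an attempt at survival data. Systematic later rejection, eGFR and proteinuria are not required, and safety reporting fills the gap only in part. The same floor applies to the non-compliance, medical-care, infection and two-rejection exits.

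The gap is clear from the text; its effect is not. Size and direction are unknown and the effect may be small. The conclusion assumes that being stopped from participating counts as withdrawal and that sites follow the written minimum. It does not assume that arms differ. It should be corrected because it touches the primary outcome and the remedy is cheap.

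**What to change.** **When and How to Withdraw Subjects, and Stopping Rules.** Replace study exit with a recorded change or stop of study medication (date, drug and reason), worded identically for both arms. Treatment decisions stay with the investigator, and the switch back to tacrolimus is unchanged.

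**Data Collection and Follow-up for Withdrawn Subjects.** Require that all such subjects, unless consent is withdrawn, are followed to 48 months from routine visits and labs for rejection, graft and patient survival, eGFR, proteinuria and aim iii events. State that study-specific leukocyte, urine biomarker and biopsy sampling is not required after the change. Keep the survival minimum for withdrawal of consent.

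**Statistical Analysis.** State that all subjects are analysed in their randomized arm.

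**Cost.** The change needs an IRB amendment and some extra data entry from visits and labs at the same centre. The analysis will include more follow-up off the assigned regimen. Subjects who stop attending the centre may still have missing data, which this change cannot prevent.
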